ICH	International Conference on Harmonisation
IRB	institutional review board
ISF	investigator site file
MedDRA	Medical Dictionary for Regulatory Activities
NAC	neutralizing antibody concentration
NOCI	new onset chronic illness
PBT	pentavalent botulinum toxoid
rBV A/B	recombinant botulinum vaccine A/B
SAE	serious adverse event
TEAE	treatment-emergent adverse events
U.S. FDA	United States Food and Drug Administration

1.0 INTRODUCTION

1.1 BACKGROUND

Botulism Immune Globulin Intravenous (Human) (BIG-IV; BabyBIG®) has been demonstrated to significantly shorten hospital stay and improve outcomes in infant botulism patients. BabyBIG is currently produced from antibodies collected from persons with existing botulinum immunity including individuals previously immunized with investigational pentavalent botulinum toxoid (PBT) for occupational protection and/or also boosted with investigational recombinant botulinum vaccine A/B (rBV A/B).

PBT was distributed through the Centers for Disease Control and Prevention (CDC) under BB-IND-0161 for occupational safety. The toxoid was administered to naïve recipients and was also administered as a booster in persons who had been previously immunized. PBT-immunized individuals who have circulating antibodies against botulinum toxin type A and type B are eligible to donate plasma for manufacture of BabyBIG. Donated plasma is fractionated and treated to yield a purified immunoglobulin G product that provides passive immunity to patients with infant botulism.

However, the CDC no longer provides investigational PBT for immunization of laboratory workers at risk for occupational exposure to botulinum serotypes A, B, C, D, and E. Specifically, on the basis of evidence of declining immunogenicity, increasing reactogenicity, and the age of the product, the CDC ceased distribution of PBT after 30 November 2011.^[1] Thus, a new immunogen against botulinum toxins is needed. A recombinant botulinum vaccine for the toxin serotypes A and B (rBV A/B) has been developed and is being proposed as a replacement vaccine for boosting participants who previously received PBT for occupational protection. This study is the second phase 2 study under IND 15155 being conducted by the California Department of Public Health (CDPH) to determine if rBV A/B will stimulate production of neutralizing antibodies against botulinum toxin types A and B in participants previously immunized with PBT (or PBT and rBV A/B). Participants with a range in neutralizing antibody titers against the toxin types would be candidates for plasma collection for BabyBIG production under IND 15155.

1.2 STUDY RATIONALE

This protocol has as its ultimate goal the production of additional lots of the approved orphan drug Botulism Immune Globulin Intravenous (Human), (BIG-IV; BabyBIG®) for the treatment of infant botulism. To enable production of BabyBIG, a group of high-titer immunized persons are needed who are willing to donate their hyperimmune plasma as a starting agent (i.e., Source Plasma) for BabyBIG. This protocol is designed to determine botulinum toxin type A and type B neutralizing antibody levels in healthy participants who were previously immunized with PBT (or PBT and rBV A/B) for occupational protection and who receive rBV A/B (or rBV A/B boost). A Phase 2b study conducted by CDPH (rBV A/B-CL-001) demonstrated a single 40- μ g dose of rBV A/B was well tolerated and resulted in a significant increase in neutralizing antibodies against botulinum toxins type A and B in participants previously immunized with PBT. The proposed study will continue to evaluate the immunogenicity and safety of a single dose of the rBV A/B vaccine in this previously immunized population. This study design is similar to rBV A/B-CL-001. However, in this study a single 40- μ g dose of rBV A/B will be used to stimulate the production of neutralizing antibodies against botulinum toxin type A and type B in participants that are rBV A/B naïve or in participants that volunteered for the rBV A/B-CL-001 clinical trial and received one dose of rBV A/B.

1.3 DOSE RATIONALE

An rBV A/B dose of 40- μ g of total antigen (20- μ g of Antigen A and 20- μ g of Antigen B) with Alhydrogel™ has been shown in Phase 1 and Phase 2 studies in healthy participants to be effective in stimulating a strong antibody response and has an acceptable safety profile. Most treatment-emergent adverse events (TEAEs) were mild and transient. Furthermore, the safety and immunogenicity of the rBV A/B vaccine in a naïve population was investigated in 372 participants using the same dose level and a three-dose schedule (under BB-IND 11756). A Phase 2b study conducted by CDPH (rBV A/B-CL-001) demonstrated a single 40- μ g dose of rBV A/B was well tolerated, and no safety concerns were identified during the study. In addition, the single 40- μ g dose resulted in a significant increase in neutralizing antibodies against botulinum toxin types A and B in participants previously immunized with PBT. Therefore, the proposed dose in this study is expected to have an acceptable safety profile and be effective in stimulating

antibody response in persons previously immunized with PBT for occupational protection.

2.0 OBJECTIVES**2.1 IMMUNOGENICITY**

The immunogenicity objective of this study is to evaluate the effects of a single 40- μ g dose of rBV A/B on the botulinum toxin type A and type B neutralizing antibody concentration (NAC) over a 12-week period following vaccination in participants previously immunized with PBT (or PBT and rBV A/B) for occupational protection.

2.2 SAFETY

The safety objective of this study is to obtain safety information during the 12-week study period and at 6 months post-vaccination on the use of rBV A/B in a population of participants previously immunized with PBT (or PBT and rBV A/B) for occupational protection.

2.3 EXPLORATORY

The exploratory objective of this study is to collect source plasma from participants that contains neutralizing antibodies against botulinum toxin type A and type B for the production of BabyBIG.

3.0 STUDY DESIGN

3.1 BASIC DESIGN CHARACTERISTICS

This will be an open-label, uncontrolled study to evaluate the safety and immunogenicity of a single intramuscular injection of 40- μ g of rBV A/B in participants who were previously immunized with PBT (or PBT and rBV A/B) for occupational protection. Participants will receive the rBV A/B injection, and may elect to undergo plasmapheresis at a maximum of two times per week up to 12 weeks. Participants can continue plasmapheresis up to 14 weeks as long as they continue to meet source plasma donor acceptance criteria. Participants will be evaluated for safety and immunogenicity at each study visit with longer-term follow-up safety data collected at 6 months.

The study period is defined as the 12-week period that includes the clinic visits and plasmapheresis visits. The study period will end at Week 4 for participants who opt not to participate or who have been determined to be ineligible for donation for the entire study. Participants undergoing plasmapheresis will also have an additional hematology specimen collected at Week 4. Study participants participating in plasma donations will have a final on-site study visit at Week 12. All participants will have a final phone call for safety follow-up at Week 26.

3.2 STUDY POPULATION

For this study, up to 50 participants are anticipated to be enrolled. Eligibility will be established by the investigator(s) on the basis of the inclusion and exclusion criteria.

3.2.1 Inclusion Criteria

To be considered eligible to participate in this study, a participant must meet the inclusion criteria listed below:

1. Have received pentavalent botulinum toxoid (or pentavalent botulinum toxoid and rBV A/B) for occupational protection under BB IND 0161 (or BB-IND-0161 and IND 015155)
2. Be 18 to 69 years old at the time of consent

3. Be healthy and have an acceptable medical history (defined as individuals who are free from significant cardiac, pulmonary, gastrointestinal, hepatic, renal, hematological, neurological, infective, muscular, infectious, rheumatic, immunological, or psychiatric diseases, as determined by medical history over the past 5 years, physical examination, and laboratory tests) that will not interfere with the objectives of the study
4. Meet the participant suitability requirements and recommendations for source plasma donors outlined in Appendix A.
5. If female, and of childbearing potential, have a negative pregnancy test at screening and within 24 hours prior to vaccination and must not plan to become pregnant until after the last plasma donation or until the Week 12 visit ([whichever occurs last]. Every female participant is considered of childbearing potential unless she has had sterilization surgery or is postmenopausal and has not had a menstrual period for at least 12 months.) If the participant is capable of childbearing, she must use a reliable form of contraception approved by investigator for 30 days before Day 0 through the end of the study. Acceptable forms of contraception include intrauterine device, birth control pills, injectable birth control, implantable birth control device, or removable birth control device or any other United States Food and Drug Administration (U.S. FDA) -approved contraceptive method, or a monogamous relationship with vasectomized partner, who has been vasectomized for 6 months or more prior to the participant's study entry, or sexual abstinence.)
6. Have the ability to understand the requirements of the study, have provided written informed consent as evidenced by signature on an informed consent form (ICF) approved by the Committee for the Protection of Human Subjects, and have agreed to abide by the study restrictions and to return for the required assessments
7. Agree to complete the participant home diary on a daily basis for 7 days post-vaccination, as well as to report any adverse events and concomitant medications during the study period
8. Have provided written authorization for use and disclosure of protected health information

9. Agree not to donate blood or blood products (outside of study procedures) until after the last plasma donation or until the Week 12 visit (whichever occurs last)

10. Have personal health insurance

3.2.2 Exclusion Criteria

To be eligible for entry into the study, the participant must not meet any of the exclusion criteria listed below:

1. Be pregnant or nursing

2. Have a history of laboratory evidence of syphilis, acquired immunodeficiency syndrome, Creutzfeldt-Jakob disease, or infection with human immunodeficiency viruses (HIV) 1 or 2, human T-cell lymphotropic virus 1, hepatitis B virus (HBV), or hepatitis C virus (HCV)

3. Have had a prior severe (Grade 3 or higher) local or severe (Grade 3 or higher) systemic reaction to last immunization with pentavalent botulinum toxoid or a prior severe immediate hypersensitivity reaction or severe systemic reaction to last vaccination on Day 0 with rBV A/B

4. Have known allergy to aluminum, yeast, or other components of the vaccine

5. Have donated one or more units of blood or undergone plasmapheresis within 49 days of the Vaccination Visit (Day 0)

6. Have received blood product or immunoglobulin within 6 months prior to study entry or plans to receive such products during the study period (exclusive of returned red blood cells as part of the plasmapheresis procedure). For participants who choose to donate plasma, this will apply until their last plasma donation or at the Week 12 visit (whichever occurs last)

7. Have received licensed nonliving vaccine within 14 days prior to study entry, or licensed live vaccine within 60 days prior to study entry

8. Have received investigational products (drugs, biologics, vaccines, or implantable devices) 60 days prior to study entry or plans to receive experimental products at any time during the study period. For participants who choose to donate plasma, this will apply until their last plasma donation or at the Week 12 visit (whichever occurs last)
9. Have received prescription immunosuppressive or immunomodulatory agents, including parenteral, inhaled, or oral corticosteroids within 3 months of study entry or plans on receiving such therapy at any time during the study period [For participants who choose to donate plasma, this will apply until their last plasma donation or at the Week 12 visit (whichever occurs last)], with the exceptions mentioned below
 - Participants who have used prescription topical steroids may be enrolled 2 weeks after the therapy is completed
 - Intra-articular, bursal, or tendon injectable steroids are permitted
 - Any over-the-counter topical steroid use is permitted
 - Ophthalmic and intranasal steroids are permitted
10. Have received cytotoxic therapy at any time in the previous 5 years before study entry
11. Have an active systemic or recurrent disease that would place the participant at unacceptable risk of injury, require hospitalization, or require surgical intervention (This includes active mental illness or history of mental illness not responsive to treatment.)
12. Have a history of alcohol or drug abuse or dependence within 12 months of study entry
13. Have past, present, or suspected illicit injection drug use
14. Have inflammatory, vasculitic, or rheumatic disease, including systemic lupus erythematosus, polymyalgia rheumatica, rheumatoid arthritis, or scleroderma

(Stable osteoarthritis treated with physical therapy and nonsteroidal anti-inflammatory drugs is not an exclusion criterion.)

15. Have any acute or chronic neuromuscular or neurologic disorder
16. Have clinically confirmed hepatic or renal insufficiency
17. Have uncontrolled hypertension, as defined a systolic blood pressure greater than 160 mmHg and diastolic blood pressure greater than 90 mmHg
18. Have moderate to severe asthma, chronic obstructive pulmonary disease, or other significant pulmonary disease
19. Have a seizure disorder
20. Have moderate or severe illness or oral temperature of 100.4°F or greater within 3 days of Vaccination Visit (Day 0)
21. Be unsuitable for participation in this study for any reason, as assessed by the investigator

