
 • Have received a blood product or immunoglobulin within 6 months of study entry or plans to receive such products during the study period (exclusive of returned red blood cells as part of the plasmapheresis procedure). For participants who choose to donate plasma, this will apply until their last plasma donation or at the Week 12 visit (whichever occurs last) • Have received licensed nonliving vaccine within 14 days prior to study entry, or licensed live vaccine within 60 days prior to study entry • Have received investigational products (drugs, biologics, vaccines, or implantable devices) within 60 days prior to study entry or plans to receive experimental products at any time during the study period. For participants who choose to donate plasma, this will apply until their last plasma donation or at the Week 12 visit (whichever occurs last) • Have received prescription immunosuppressive or immunomodulatory agents, including parenteral, inhaled, or oral corticosteroids within 3 months of study entry or plans on receiving such therapy at any time during the study period. For participants who choose to donate plasma, this will apply until their last plasma donation or at the Week 12 visit (whichever occurs last) with the exceptions mentioned below: 
 ○ Participants who have used prescription topical steroids may be enrolled 2 weeks after the therapy is completed ○ Intra-articular, bursal, or tendon injectable steroids are permitted ○ Any over-the-counter topical steroid use is permitted ○ Ophthalmic and intranasal steroids are permitted • Have received cytotoxic therapy at any time in the previous 5 years before study entry • Have an active systemic or recurrent disease that would place the participant at unacceptable risk of injury, require hospitalization, or require surgical intervention (This includes active mental illness or history of mental illness not responsive to treatment.) • Have a history of alcohol or drug abuse or dependence within 12 months of study entry • Have past, present, or suspected illicit injection drug use • Have inflammatory, vasculitic, or rheumatic disease, including systemic lupus erythematosus, polymyalgia rheumatica, rheumatoid arthritis, or scleroderma (Stable osteoarthritis treated with physical therapy and nonsteroidal anti-inflammatory drugs is not an exclusion criterion.) • Have any acute or chronic neuromuscular or neurologic disorder • Have clinically confirmed hepatic or renal insufficiency • Have uncontrolled hypertension, as defined as systolic blood pressure greater than 160 mmHg and diastolic blood pressure greater than 90 mm Hg • Have moderate to severe asthma, chronic obstructive pulmonary disease, or other significant pulmonary disease • Have a seizure disorder • Have moderate or severe illness or oral temperature of 100.4°F or greater within 3 days prior to Vaccination Visit (Day 0) • Be unsuitable for participation in this study for any reason, as assessed by the investigator

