3.5 REPLACEMENT OF DROPOUTS

Dropouts will not be replaced in this study.

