5.2.2.1 Vaccination Visit (Week 0, Day 0)

During this visit, the following activities will occur:

- Review of baseline health assessment and inclusion and exclusion criteria
- Urine pregnancy test for female participants of childbearing potential, performed within 24 hours preceding receipt of the study vaccine.
- Collection of 20 mL of blood to determine NAC
- Vital signs (temperature, blood pressure, heart rate, and respiratory rate) assessed before the injection and 30 minutes (\pm 5 minutes) after the injection
- Injection of rBV A/B
- Participant monitored for at least 30 minutes after injection for localized and systemic reactions, including vital signs taken at the end of the 30-minute period
- Reaction Recording Sheet – Participant Home Diary distributed to the participant to record injection site information and systemic reactions, if any, as well as concomitant medications taken for potential reactions (copy of diary is in Appendix C)
- Adverse Event Recording Sheet for Identification of Possible Serious Adverse Events distributed to the participant to record adverse events, for 7 days (copy of recording sheet is in Appendix E)

Total blood volume collected at this visit will be 20 mL for NAC.

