APPENDIX A

CODE OF FEDERAL REGULATIONS PART 640: ADDITIONAL STANDARDS FOR HUMAN BLOOD AND BLOOD PRODUCTS

**CODE OF FEDERAL REGULATIONS PART 640—ADDITIONAL STANDARDS
FOR HUMAN BLOOD AND BLOOD PRODUCTS****Subpart G—Source Plasma****§ 640.63 Suitability of donor.**

- (a) *Method of determining.* The suitability of a donor for Source Plasma will be determined by a qualified licensed physician or by persons under his or her supervision and trained in determining donor suitability. Such determination will be made on the day of collection from the donor by means of a medical history, tests, and such physical examination as appears necessary to the qualified licensed physician.
- (b) *Initial medical examinations.*
 - (1) Each donor will be examined by a qualified licensed physician on the day of the first donation or no more than 1 week before the first donation and at subsequent intervals of no longer than 1 year.
 - (2)
 - (i) A donor who is to be immunized for the production of high-titer plasma will be examined by a qualified licensed physician. The medical examination will be performed within no more than 1 week before the first immunization injection. The medical examination for plasmapheresis need not be repeated, if the first donation occurs within 3 weeks after the first injection.
 - (ii) A donor who is an active participant in a plasmapheresis program, and has been examined in accordance with paragraph (b)(1) of this section, need not be reexamined before immunization for the production of high-titer plasma.
 - (3) Each donor will be certified to be in good health by the examining physician. The certification of good health will be on a form supplied by the licensed establishment and will indicate that the certification applies to the suitability of the individual to be a plasmapheresis donor and, when applicable, an immunized donor.

(c) *Qualification of donor.* Donors will be in good health on the day of donation, as indicated in part by:

- (1) Normal temperature;
- (2) Demonstration that systolic and diastolic blood pressures are within normal limits, unless the examining physician is satisfied that an individual with blood pressures outside these limits is an otherwise qualified donor under the provisions of this section;

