APPENDIX B

TOXICITY TABLES FROM GUIDANCE FOR INDUSTRY: TOXICITY GRADING SCALE FOR HEALTHY ADULT AND ADOLESCENT PARTICIPANTS ENROLLED IN PREVENTIVE VACCINE CLINICAL TRIALS

Table 6. Clinical Abnormalities from Vital Signs

Vital Signs ^a	Mild (Grade 1)	Moderate (Grade 2)	Severe (Grade 3)	Potentially Life Threatening (Grade 4)
Fever (°C) ^b (°F) ^b	38.0-38.4 100.4-101.1	38.5-38.9 101.2-102.0	39.0-40.0 102.1-104.0	>40.0 >104.0
Tachycardia (beats per minute)	101-115	116-130	>130	ER visit or hospitalization for arrhythmia
Bradycardia ^c (beats per minute)	50-54	45-49	<45	ER visit or hospitalization for arrhythmia
Hypertension: systolic (mm Hg)	141-150	151-155	>155	ER visit or hospitalization for malignant hypertension
Hypertension: diastolic (mm Hg)	91-95	96-100	>100	ER visit or hospitalization for malignant hypertension
Hypotension: systolic (mm Hg)	85-89	80-84	<80	ER visit or hospitalization for hypotensive shock
Respiratory rate (breaths per minute)	17-20	21-25	>25	Intubation

ER = emergency room.

a Participant should be at rest for all vital sign measurements.

b Oral temperature should be taken, and there should be no consumption of recent hot or cold beverages or smoking.

c Use clinical judgment when characterizing bradycardia among some healthy participant populations, for example conditioned athletes.

Table 7. Systemic Clinical Abnormalities

Systemic (General)	Mild (Grade 1)	Moderate (Grade 2)	Severe (Grade 3)	Potentially Life Threatening (Grade 4)
Nausea/vomiting	No interference with activity, or 1 to 2 episodes per 24 hours	Some interference with activity or >2 episodes per 24 hours	Prevents daily activity, requires outpatient intravenous hydration	ER visit or hospitalization for hypotensive shock
Diarrhea	2 to 3 loose stools or <400 g per 24 hours	4 to 5 stools or 400 to 800 g per 24 hours	6 or more watery stools or >800 g per 24 hours or requires outpatient intravenous hydration	ER visit or hospitalization
Headache	No interference with activity	Repeated use of nonnarcotic pain reliever >24 hours or some interference with activity	Significant; any use of narcotic pain reliever or prevents daily activity	ER visit or hospitalization
Fatigue	No interference with activity	Some interference with activity	Significant; prevents daily activity	ER visit or hospitalization
Myalgia	No interference with activity	Some interference with activity	Significant; prevents daily activity	ER visit or hospitalization

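### Exclusion 17 requires both blood pressure limits to be exceeded, so a reading with only one pressure clearly high does not meet the protocol's only numeric blood pressure exclusion

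*Protocol*

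**What the plan says.** Protocol 3.2.2, item 17, excludes people with uncontrolled hypertension and defines the term as "systolic blood pressure greater than 160 mmHg and diastolic blood pressure greater than 90 mmHg". The exclusion list in the Synopsis uses the same conjunction: "systolic blood pressure greater than 160 mmHg and diastolic blood pressure greater than 90 mm Hg".

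Four other entry criteria could bear on a high reading, and none states a blood pressure value:

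- Inclusion 3 requires good health and freedom from significant cardiac disease, among others, judged from history, examination and laboratory tests.
- Inclusion 4 is worded "Meet the participant suitability requirements and recommendations for source plasma donors outlined in Appendix A". In that appendix, 640.63(c)(2) asks for "Demonstration that systolic and diastolic blood pressures are within normal limits, unless the examining physician is satisfied" that a person outside those limits is otherwise a qualified donor.
- Exclusion 11 covers active systemic or recurrent disease that would put the participant at unacceptable risk.
- Exclusion 21 lets the investigator judge anyone unsuitable for any reason.

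At the vaccination visit (Protocol 5.2.2.1) the inclusion and exclusion criteria are reviewed. The same visit lists "Vital signs (temperature, blood pressure, heart rate, and respiratory rate) assessed before the injection and 30 minutes" after it. Appendix B Table 6 gives numeric hypertension grades, with separate rows for systolic and diastolic pressure. These are toxicity grades and exclude nobody.

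**The concern.** A numeric exclusion for uncontrolled hypertension should identify a person whose systolic or diastolic pressure is far too high. Item 17 identifies only people who pass both limits. Because it is written as a definition, it also tells site staff that 200/85 is not uncontrolled hypertension for the purposes of this study.

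What is at stake is entry safety in healthy volunteers aged up to 69, some of whom go on to repeated plasmapheresis, and consistent application at the two sites. Blood pressure is measured just before injection, yet the one rule with numbers gives no instruction to stop when a single pressure is high. The immunogenicity results are not at stake.

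**Working it through.** No sample size or error rate is involved. The check evaluates the criterion as a logical rule.

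**Inputs**

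- Item 17 (Protocol 3.2.2 and Synopsis): excluded if S > 160 and D > 90, both limits strict.
- Alternative: excluded if S > 160 or D > 90.
- Table 6 (Appendix B), systolic: 141–150 mild, 151–155 moderate, above 155 severe.
- Table 6, diastolic: 91–95 mild, 96–100 moderate, above 100 severe.

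**Individual readings**

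| Reading | Item 17 as written | With *or* | Systolic grade | Diastolic grade |
|---|---|---|---|---|
| 161/91 | excluded | excluded | severe | mild |
| 200/85 | not excluded | excluded | severe | none |
| 150/120 | not excluded | excluded | mild | severe |
| 150/100 | not excluded | excluded | mild | moderate |
| 120/91 | not excluded | excluded | none | mild |
| 160/90 | not excluded | not excluded | severe | none |

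The first three rows show the problem. 161/91 is excluded, while 200/85 and 150/120 are not.

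**Size of the gap in the rule**

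Systolic at or below 160 or above it, crossed with diastolic at or below 90 or above it, gives 2 × 2 = 4 combinations. *And* excludes one and *or* excludes three. The gap is the 3 − 1 = 2 combinations in which exactly one limit is passed.

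- S > 160 with D ≤ 90: every such reading is severe in Table 6, because any systolic value above 160 is above 155.
- S ≤ 160 with D > 90: the grades are mixed. A reading here is severe if S is 156–160 or D is above 100. It is not severe on either pressure exactly when S ≤ 155 and D is 91–100. Examples are 120/91 and 150/100.

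These combinations describe the rule. They do not say how many candidates have such readings, and the documents give no blood pressure distribution from which to estimate it.

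**The case against.** The strongest reply is that nobody with 200/85 need be vaccinated. Exclusion 21 alone permits refusal, and Inclusion 3 and Exclusion 11 give further grounds. Inclusion 4 is mandatory, and its donor rule covers each pressure and expects both to be normal by default. The exception is a real clinical judgement: the physician must be satisfied that the person is otherwise a qualified donor. Appendix A also requires a physician's examination within a week before the first immunization (active donors already examined are exempt) and certification of good health. Eligibility is reviewed at the same visit as the pre-injection reading.

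This stands, and it limits the point. A reader might infer that the protocol admits people with severe single-pressure hypertension unchecked. The documents do not support that, because several criteria allow refusal. What remains is that each depends on judgement without a stated value, and the donor rule can be set aside for an individual. Rule (c) is also framed around the day of donation, and donor eligibility is confirmed at the collection center after vaccination (Protocol 5.2.2.2). The only objective blood pressure limit still misses the readings it should catch.

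A second reply is that *or* with the present limits overcorrects: it would label 120/91 uncontrolled hypertension although Table 6 calls that diastolic value mild. This also stands. It means the diastolic limit needs a clinical decision, and it is no argument for keeping *and*.

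A third is that no harm from a single dose at a raised pressure is shown. That is correct, and it is a reason to rate the point low.

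**Conclusion.** Wrong as written; a minor entry-safety point. Item 17 and its copy in the Synopsis miss every reading in which only one limit is passed, including readings that are severe on the protocol's own scale. The gap lies in the objective rule. Other criteria narrow it, and enrolment of such a person is not assured.

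Three stronger conclusions might be inferred and are not supported:

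- That the trial's results are affected. SAP 8.4 only lists vital signs, and no immunogenicity endpoint or planned safety analysis depends on this criterion.
- That a known number of participants is exposed. Nothing in the documents allows that count among up to 50.
- That 160/110 is a clean example of isolated diastolic hypertension. It does escape item 17, but a systolic pressure of 160 is itself severe in Table 6. 200/85 and 150/120 show the gap without that complication and away from the strict limits.

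The conclusion assumes that item 17 is applied literally, and that it was meant to catch a marked rise in either pressure. The separate rows in Table 6 and the donor rule's reference to both pressures fit that intent, but the protocol does not state it.

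**What to change.** In Protocol 3.2.2 item 17 and in the Synopsis, define uncontrolled hypertension as systolic pressure above 160 mmHg **or** diastolic pressure above 90 mmHg. Before the edit is final, the medical monitor should confirm the diastolic limit. If 90 is too strict as a stand-alone limit, set a higher one and keep *or*.

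Costs:

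- Some additional screen failures. With the limit at 90 these include people with systolic at or below 155 and diastolic 91–100, whom Table 6 grades no worse than moderate. The default donor rule may already question many of them. The pool is finite, since entry requires earlier pentavalent toxoid and "the CDC ceased distribution of PBT after 30 November 2011".
- A protocol amendment. Protocol 9.4 treats a change in selection criteria as substantive, needing approval by the sponsor-investigator and the IRB and submission to the regulatory authority. It can be combined with other changes.

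No endpoint, analysis population or planned table has to change.
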